6.6.3 Dose Modifications for Non-haematological Toxicities

Dose modifications for non-haematological toxicities may occur at any time and the management are shown [Table 7](#) toxicities are graded according to CTCAE version 5. Special considerations for TLS and specific AEs are included in [Appendix F](#).

Dose modifications for changes in hepatic biochemistry are summarised in Section [6.6.4](#).

If a patient experiences a clinically significant and/or unacceptable non-haematological toxicity (including a DLT), considered by the Investigator to be related to study treatment, and not attributable to the disease (or to disease-related processes) under investigation, dosing will be withheld or the dose reduced and supportive therapy administered as required.

Table 7 Dose Modifications for Non-haematological Toxicities

Event	Occurrence	Action with AZD0466
Non-haematological Toxicities (except hepatic and cardiac changes, see Sections 6.6.4 and 6.6.5)		
CTCAE Grade 1 non-haematological toxicities	Any	None
CTCAE Grade 2 non-haematological toxicities	First occurrence	None
	Second and subsequent occurrences	
 Withhold AZD0466 until resolution to CTCAE Grade ≤ 1 or baseline. Maximum dose hold 21 days. Restart AZD0466 at same dose level if at target dose or dose escalate if at ramp-up. For > 3 occurrences, consider restarting AZD0466 at one lower dose level if at target or consider to discontinue if at ramp-up.

Table 7 Dose Modifications for Non-haematological Toxicities

Event	Occurrence	Action with AZD0466
CTCAE Grade 3 non-haematological toxicities	First occurrence	
 Withhold AZD0466 until resolution to CTCAE Grade \leq 1 or baseline. Supportive therapy should be given as per institutional guidelines. If resolution occurs in \leq 7 days, restart AZD0466 at the same dose level if at target or dose escalate if at ramp-up, after discussion with Medical Monitor. If no resolution in \leq 7 days, withhold AZD0466 for up to a total of 21 days. If resolution occurs in $>$ 7 days but \leq 21 days, restart AZD0466. At one lower dose level if at target or consider to discontinue if at ramp-up. Discontinue AZD0466 if no resolution to CTCAE Grade \leq 1 in $<$ 21 days
	Second and subsequent occurrences	
 Withhold AZD0466 and provide supportive therapy as per institutional guidelines. Discontinue if at ramp-up. If at target and resolution occurs in \leq 7 days: restart AZD0466 at one lower dose after discussion with Medical Monitor. If no resolution in \leq 7 days, withhold AZD0466 for up to a total of 21 days. If resolution to CTCAE \leq Grade 1 occurs within 21 days, discuss with Investigator and Medical Monitor to further dose reduce by one dose level from previous dose, and to continue treatment if the patient is deriving clinical benefit. Discontinue AZD0466 if no resolution to CTCAE Grade \leq 1 in \leq 21 days.
CTCAE Grade 4 non-haematological toxicities	Any	
 Discontinue AZD0466.

CTCAE, Common Terminology Criteria for Adverse Events (Version 5)

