5.2 Core Exclusion Criteria

The exclusion criteria that are applicable to all modules in the study are described in this section. Please refer to the individual modules for additional module-specific exclusion criteria.

Patients must not enter the study if any of the following criteria are fulfilled:

Medical Conditions

- 1 Unresolved toxicity from prior anticancer therapy of Common Terminology Criteria for Adverse Events (CTCAE) Grade ≥ 2 . Patients with Grade 2 neuropathy or Grade 2 alopecia are eligible.
- 2 Active idiopathic thrombocytopenic purpura.
- 3 Haemopoietic stem cell transplant < 100 days prior to the first dose of study treatment.
- 4 Immunosuppression for graft versus host disease (GVHD) or GVHD prophylaxis within 4 weeks prior to the first dose of study treatment. The following are **permitted**:
 - (a) topical steroids for GVHD may continue indefinitely
 - (b) systemic steroids for GVHD up to 2 weeks prior to the first dose of study treatment
 - (c) Treatment with high-dose steroids (ALL and leukaemia of ambiguous lineage) for white blood cell count control is permitted during screening, and in Cycle 1 up to 4 days (maximum dexamethasone IV 40 mg/day or equivalent). It can be started or stopped at any point during this period.
- 5 Active central nervous system (CNS) leukaemia/leptomeningeal disease/spinal cord compression. Patients who have a history of CNS leukaemia must be free of CNS leukaemia for > 30 days prior to the first dose of study treatment, and the most recent 2 lumbar punctures must be negative for leukaemic cells, to be eligible.
- 6 Known history of infection with human immunodeficiency virus (HIV).
- 7 Known serologic status reflecting active hepatitis B or C infection.
 - (a) Patients who are anti-HBc antibody positive and who are surface antigen negative will need to have a negative polymerase chain reaction (PCR) result before enrolment. Those who are hepatitis B surface antigen positive or hepatitis B PCR positive will be excluded.
 - (b) Patients who are hepatitis C antibody positive will need to have a negative PCR result before enrolment. Those who are hepatitis C PCR positive will be excluded.
- 8 Known uncontrolled infection with cytomegalovirus (CMV).

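### Table 7, Grade 3 first occurrence: the restart lines accept a return to baseline but the discontinue line does not, so an eligible patient with Grade 2 neuropathy can meet both

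*Protocol*

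**What the plan says.** Protocol Section 6.6.3, Table 7, covers "Non-haematological Toxicities (except hepatic and cardiac changes, see Sections" 6.6.4 and 6.6.5), so neuropathy falls within it. The Grade 3 first-occurrence cell contains four relevant instructions:

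- Hold: withhold until Grade ≤ 1 "or baseline. Supportive therapy should be given as per institutional guidelines".
- Resolution in ≤ 7 days: "restart AZD0466 at the same dose level if at target or dose escalate if at ramp-up, after discussion with Medical Monitor".
- Resolution in > 7 but ≤ 21 days: restart, "at one lower dose level if at target or consider to discontinue if at ramp-up".
- Last bullet: "Discontinue AZD0466 if no resolution to CTCAE Grade" ≤ 1 in < 21 days. Baseline is not mentioned.

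The row for second and subsequent Grade 3 occurrences opens with "Withhold AZD0466 and provide supportive therapy as per institutional guidelines". It has no baseline alternative anywhere. Its 7-day limb refers to resolution without giving a grade, and its 21-day limbs use Grade ≤ 1, with the discontinue line set at ≤ 21 days.

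Protocol Section 5.2, exclusion criterion 1, bars unresolved toxicity of Grade ≥ 2 from prior anticancer therapy, with an exception: "Patients with Grade 2 neuropathy or Grade 2 alopecia are eligible".

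**The concern.** The hold line and the discontinue line of one cell use different recovery targets, and the eligibility criteria admit patients for whom those targets differ. For such a patient, one line returns the patient to study drug and another ends treatment permanently.

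Three things depend on which line a site follows:

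- The patient is either re-exposed or taken off therapy.
- SAP Section 4.6.2.1, Deviation 2, makes it an important protocol deviation to meet discontinuation criteria and stay on AZD0466. A site that followed the restart line could be recorded as deviating under the last bullet.
- SAP Section 4.14.4 tabulates adverse events leading to discontinuation, so the same clinical course could be counted differently at two sites.

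**Working it through.** No formula applies and the plan states no figure to reproduce. The check is to apply the cell's lines to defined cases.

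**Inputs.** The hold, restart and discontinue lines of the Grade 3 first-occurrence cell (Table 7), and baseline Grade 2 neuropathy allowed by exclusion criterion 1 (Section 5.2). The restart bullets say only that resolution has occurred. Resolution is given the meaning set by the opening bullet of the same cell, which is Grade ≤ 1 or baseline.

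**Case 1: baseline Grade 2 neuropathy, first treatment-related Grade 3, recovery to Grade 2 but not Grade 1.**

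| Recovery to Grade 2 | Stage | Hold and restart lines | Last bullet | Conflict |
|---|---|---|---|---|
| By day 7 | Target dose | Restart, same dose | Discontinue | Yes |
| By day 7 | Ramp-up | Continue escalation | Discontinue | Yes |
| Days 8 to 21 | Target dose | Restart, one level lower | Discontinue | Yes |
| Days 8 to 21 | Ramp-up | Discontinuation to be considered | Discontinue | Slight |

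**Case 2: baseline Grade 0 or 1.** Grade ≤ 1 or baseline is then the same condition as Grade ≤ 1, so the two targets coincide and the baseline conflict does not arise.

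**Case 3: any baseline, recovery to Grade ≤ 1 on exactly day 21.** The restart limit (≤ 21) is met. The event did not resolve in < 21 days, so the last bullet is also triggered. This overlap is one day wide. The repeat-occurrence row uses ≤ 21 in its discontinue line, so the two Grade 3 rows also differ on the limit.

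**Does other text settle it?** The instruction to contact the Medical Monitor for scenarios not described follows Table 6 in Section 6.6.2. It concerns undescribed scenarios, whereas this one is described twice. The 7-day restart bullet requires a discussion with the Medical Monitor but does not say that the discussion overrides the discontinue line. Section 8 sends immediate safety concerns to the Medical Monitor for a decision to continue or stop, but also disallows protocol waivers. Table 8 (Section 6.6.4) shows that the intent can be written consistently: its first-listed event uses the same two-part target in the hold lines and in the third-occurrence restart condition.

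**The case against.** The best defence is that the cell is meant to be read in order. The first bullet sets the target, the next bullets restart on resolution, and the last bullet closes a hold that has failed. On that reading a patient restarted on day 5 is no longer on hold when the last bullet applies, and the missing baseline alternative is shorthand. This may well be what was intended. But the last bullet restates its own target as Grade ≤ 1 and is not limited to patients still on hold. The opposite reading, that resolution means Grade ≤ 1 throughout, leaves the baseline alternative in the first bullet with no effect. Each reading sets aside some of the text, so the mismatch stands.

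Several stronger inferences are tempting and are not supported:

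- That every patient with a Grade 2 baseline is affected. The event must worsen to Grade 3, be judged related to study treatment and not to the disease, be a first occurrence, and recover to Grade 2 but no further.
- That such a patient can never reach Grade 1. The protocol only says that Grade 2 neuropathy is eligible; it does not say that it cannot improve.
- That the repeat-occurrence row is wrong because it is stricter. A stricter standard for a repeat event could be deliberate. What can be said is that its 7-day limb leaves resolution undefined.
- That discontinuation rates are inflated. Nothing in the documents shows this. The planned Part B interim safety rule (Section 11.7.9) reacted to 4 or more discontinuation events in 12 patients, where one classification moves the rate by 1/12 = 8.3 percentage points. SAP Section 1 records that Part B was not initiated.

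The day-21 point turns on a single symbol. The same cell permits a hold of up to 21 days in total, and the Grade 2 row sets a 21-day maximum hold, which suggests that day 21 was meant to be included. The symbol should be checked against the signed protocol, and the point is best treated as typographical.

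**Conclusion.** The concern holds in a narrow form. The Grade 3 first-occurrence cell of Table 7 gives opposite instructions for a patient the protocol expressly admits, and no other section resolves them. The clash is clear at target dose, and at any stage when recovery comes within 7 days. It is slight for ramp-up patients recovering on days 8 to 21.

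The number of patients affected cannot be derived from the documents, which give no frequency of baseline Grade 2 neuropathy or of its worsening. With recruitment stopped and the study terminated (SAP Section 1), the practical consequences are consistent classification of deviations and discontinuations in reporting, and the risk of carrying the table into a later protocol. This is a minor point about an operative rule and does not challenge any estimate.

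The conclusion assumes that resolution in the restart bullets carries the meaning given in the opening bullet. The day-21 remark further assumes that the < sign is as printed.

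**What to change.** Reconcile the hold, restart and discontinue lines in the Table 7 Grade 3 cells. Each cell should state one resolution target and one day limit and use them in all its lines. The repeat-occurrence row should say what resolution means in its 7-day limb. The result should then be checked against exclusion criterion 1, so that patients admitted with a Grade 2 baseline are covered without ambiguity. Which target and which limit apply is a clinical decision for the sponsor, and this point takes no position on it.

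The cost is a wording change in one protocol table. For the existing data, the sponsor could record before applying SAP Deviation 2 which reading was used, and apply it to every case.

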6.6.4 Dose Modifications for Hepatotoxicity

AZD0466 dosing should be modified if a patient with normal or abnormal baseline liver function experiences a clinically significant and/or unacceptable change in hepatic biochemistry (including a DLT) described in [Table 8](#) that is considered by the Investigator to be related to study treatment and not attributable to the disease (or to disease-related processes) under investigation.

Table 8 Dose Modification for Hepatotoxicity

Event	Occurrence	Action with AZD0466
For patients with normal baseline liver function: ALT and/or AST > 5 × ULN and ≤ 8 × ULN without concomitant elevation in bilirubin, which return to baseline within 7 days OR For patients with abnormal baseline liver function: ALT and/or AST > 5 × baseline and ≤ 8 × baseline or ALT and/or AST > 7 × ULN and ≤ 10 × ULN, (whichever is lower in × ULN), without concomitant elevation in bilirubin, which return to baseline levels within 7 days	First occurrence	
 Withhold AZD0466 until values return to CTCAE Grade ≤ 1 or baseline. Restart AZD0466 at same dose level if at target or dose escalate if at ramp-up.
	Second occurrence	
 Withhold AZD0466 until values return to CTCAE Grade ≤ 1 or baseline. Restart AZD0466 at one lower dose if at target or consider to discontinue if at ramp-up.
	Third occurrence	
 Withhold AZD0466 until values return to CTCAE Grade ≤ 1 or baseline. Discontinue if at ramp-up. If at target dose: Restart AZD0466 at one lower dose than the current dose if all values resolve to baseline or Grade ≤ 1 within 7 days and there is clear evidence of clinical benefit. A Q2W schedule may be considered. Discontinue AZD0466 if the above criteria are not met.
For patients with normal baseline liver function: ALT and/or AST > 8 × ULN and ≤ 20 × ULN without concomitant elevation in bilirubin, which return to baseline or Grade 1 levels within 14 days OR For patients with abnormal baseline liver function: ALT and/or AST > 8 × baseline and ≤ 20 × baseline or ALT and/or AST > 10 × ULN and ≤ 20 × ULN, (whichever is lower in x ULN), without concomitant elevation in bilirubin, which return to baseline or Grade 1 levels within 14 days	First occurrence	
 Withhold AZD0466 until values return to CTCAE Grade ≤ 1 or baseline. Consider to discontinue if at ramp-up. If at target dose: Restart AZD0466 at one lower dose than the current dose.
	Second occurrence	
 Withhold AZD0466 until values return to CTCAE Grade ≤ 1 or baseline. Discontinue if at ramp-up and not previously stopped. If at target dose: Restart AZD0466 at one lower dose than the current dose and consider Q2W dosing schedule.
	Third occurrence	
 Withhold AZD0466 until values return to CTCAE Grade ≤ 1 or baseline. Restart AZD0466 at 2 lower dose levels than current dose and resume on a Q2W schedule, if all values resolve to baseline or CTCAE Grade ≤ 1 within 14 days and there is clear evidence of clinical benefit. Discontinue AZD0466 if the above criteria are not met.

Table 8 Dose Modification for Hepatotoxicity

Event	Occurrence	Action with AZD0466
For patients with normal baseline liver function: ALT and/or AST $\geq 3 \times$ ULN with concomitant elevation in bilirubin $\geq 2 \times$ ULN OR For patients with abnormal baseline liver function: ALT and/or AST $\geq 3 \times$ baseline with concomitant elevation in bilirubin $\geq 2 \times$ baseline	Any occurrence	
 Discontinue AZD0466, refer to Appendix E for process to follow in order to identify and appropriately report episodes of potential Hy's Law.
ALT and/or AST $> 20 \times$ ULN	Any occurrence	
 Discontinue AZD0466.

ALT, alanine aminotransferase; AST, aspartate aminotransferase; CTCAE, common terminology criteria for adverse events; ULN, upper limit of normal; Q2W, every 14 days

6.6.5 Cardiac findings

AZD0466 should be withheld if any of the following occur at any time during study treatment:

- Symptomatic tachycardia
- Symptomatic hypotension
- QTcF shortening by 60 milliseconds compared to baseline, or interval value < 340 milliseconds, confirmed on at least 2 separate ECGs recorded 5 minutes apart
- QTcF prolongation of > 500 milliseconds or QTcF prolongation from baseline by 60 milliseconds, confirmed on at least 2 separate ECGs recorded 5 minutes apart
- Any other cardiac findings of CTCAE Grade ≥ 2 if considered by the Investigator to be clinically significant

AZD0466 should be permanently discontinued if a CTCAE \geq Grade 3 cardiac AE of any duration occurs during study treatment, if considered by the Investigator to be related to study treatment.

Patients should be monitored closely including continuous ECG monitoring as clinically indicated (including for QTcF prolongations > 500 milliseconds) and until such a time as deemed safe to discontinue monitoring by medical review, with cardiologist input considered in the instance of abnormal ECG findings. AZD0466 may be restarted after resolution of

cardiac findings to the patient's baseline at the discretion of the Investigator and after discussion with the Medical Monitor.

6.6.6 Infusion-site reactions

As with other drugs administered intravenously, local infusion-site reactions (eg infusion pain, infusion-site reaction, skin irritation, or vein irritation) may occur. For CTCAE Grade ≥ 2 reactions, the infusion of AZD0466 should be stopped; if the patient recovers without issue, a full dose may be considered at the next scheduled infusion. For CTCAE Grade 1 or transient reactions with recovery within 15 minutes, AZD0466 infusion may be restarted if timings permit it to be completed within the 3-hour window of stability.

6.7 Dose-limiting Toxicity

Refer to Module 1 (Section [11.4.7](#)).

6.7.1 Definition of Maximum Tolerated Dose

Maximum tolerated dose will be determined using the modified toxicity probability interval (mTPI-2) approach as described in Module 1 (Section [11.4.7.3](#))

6.7.2 Definition of Recommended Phase II Dose

Refer to Module 1 (Section [11.4.7.4](#)).

6.7.3 Definition of Maximum Feasible Dose

Refer to Module 1 (Section [11.4.7.5](#)).

6.7.4 Safety Review Committee

Refer to Appendix [A 5](#).

6.8 Treatment After the End of Study

Patients are permitted to receive further therapy or may continue to receive study treatment following the end of the study if, in the opinion of the Investigator, they are continuing to receive benefit from treatment. After discontinuation of study treatment, the Investigator will be at liberty to define further the most appropriate anticancer treatment.

Subsequent anticancer treatment is expected to be initiated following the cancer recurrence or development of a new cancer. Information on subsequent anticancer therapies should be recorded on the clinical database.

7 DISCONTINUATION OF STUDY TREATMENT AND PATIENT DISCONTINUATION/WITHDRAWAL - CORE

7.1 Discontinuation of Study Treatment

Patients who permanently discontinue study treatment will continue to have follow-up assessments per the SoA. Patients will be permanently discontinued from study treatment if the following criteria are met:

- Patient decision. The patient is at any time free to discontinue study treatment, without prejudice to further treatment. A patient who discontinues study treatment is normally expected to continue to participate in the study (eg, for safety and survival follow-up) unless they specifically withdraw their consent to all further participation in any study procedures and assessments.
- Investigator decision
- Occurrence of any AE that, in the opinion of the Investigator or AstraZeneca contraindicates further dosing
- Pregnancy or intent to become pregnant
- Patients incorrectly initiated on study treatment (Section 7.1.2)
- Severe noncompliance with the study protocol that, in the opinion of the Investigator or AstraZeneca, warrants withdrawal from study treatment (eg, refusal to adhere to scheduled visits)
- The discovery of an unexpected, significant, or unacceptable risk to the patients enrolled in the study
- Decision to modify the development plan of the drug
- Initiation of alternative anticancer therapy including another investigational agent
- Confirmed disease progression ([Appendix J](#) and [Appendix K](#))
- Death

All patients who are discontinued from study treatment should complete protocol-specified procedures for discontinuation of study treatment and follow-up procedures. Discontinued patients will be followed for survival, either through direct contacts or by collecting public records (eg, death certificates) as allowed by local laws.

The end of treatment (EoT) visit should be performed as soon as the patient is permanently discontinued from study treatment. The reason for discontinuation should be documented in the source document and the appropriate section of the eCRF.

Patients may withdraw from any aspects of the optional exploratory research at any time,

without prejudice to further treatment and independent of any decision concerning participation in other aspects of the main study. Procedures for withdrawal from the exploratory research are outlined in Appendix [C 2](#).

7.1.1 Procedures for Discontinuation of Study Treatment

Discontinuation of study treatment does not affect the patient's participation in the study. A patient who decides to discontinue the study treatment will always be asked about the reason(s) for discontinuation and the presence of any AE. The patient should continue attending subsequent study visits, and data collection should continue according to the study protocol. If the patient does not agree to continue to attend study visits in person, where possible, a modified follow-up must be arranged to ensure the collection of endpoints and safety information. The approach taken should be recorded in the medical records. A patient that agrees to modified follow-up is not considered to have withdrawn consent or to have withdrawn from the study.

Patients who are permanently discontinued from further receipt of study treatment, regardless of the reason, will be identified as having permanently discontinued treatment, followed by entry into follow-up. Patients who have permanently discontinued from further receipt of study treatment will need to be recorded in the IRT.

All patients will be followed for survival until the end of the study. Survival information may be obtained via telephone contact with the patient, patient's family, or by contact with the patient's current physician. Patients who decline to return to the site for evaluations should be contacted by telephone, following the timing and procedures indicated in the SoA, as an alternative.

